Appendix 12 Preferred Term Examples for AESIs

Gastrointestinal non-specific symptoms and therapeutic procedures (SMQ-narrow)

Abdominal discomfort Abdominal distension Abdominal pain Abdominal pain lower Abdominal pain upper Abdominal symptom Abdominal tenderness Abnormal faeces Aerophagia Anorectal discomfort Bowel movement irregularity Change of bowel habit Constipation Defaecation urgency Diarrhoea Epigastric discomfort Eructation Faecal volume decreased Faecal volume increased Faeces hard Faeces soft Flatulence Frequent bowel movements Gastrointestinal pain Gastrointestinal sounds abnormal Gastrointestinal toxicity Infrequent bowel movements Nausea Non-cardiac chest pain Oesophageal discomfort Oesophageal pain Premenstrual cramps Vomiting

Supraventricular tachyarrhythmias (SMQ-narrow)

Arrhythmia supraventricular Atrial fibrillation Atrial flutter Atrial parasystole Atrial tachycardia Junctional ectopic tachycardia Sinus tachycardia Supraventricular extrasystoles Supraventricular tachyarrhythmia Supraventricular tachycardia

Haematopoietic cytopenias (SMQ-narrow)
Haematopoietic cytopenias affecting more than one type of blood cell (SMQ-narrow)
Aplastic anaemia Autoimmune aplastic anaemia Bicytopenia Bone marrow failure Cytopenia Febrile bone marrow aplasia Full blood count decreased Gelatinous transformation of the bone marrow Pancytopenia Panmyelopathy
Haematopoietic erythropenia (SMQ-Narrow)
Anaemia macrocytic Aplasia pure red cell Aplastic anaemia Erythroblast count decreased Erythroid maturation arrest Erythropenia Hypoplastic anaemia Microcytic anaemia Proerythroblast count decreased Red blood cell count decreased Reticulocyte count decreased Reticulocytopenia
Haematopoietic leukopenia (SMQ-Narrow)
Agranulocytosis B-lymphocyte count decreased Band neutrophil count decreased Band neutrophil percentage decreased Basophil count decreased Basophilopenia Cyclic neutropenia Eosinopenia Eosinophil count decreased Febrile neutropenia Granulocyte count decreased Granulocytes maturation arrest Granulocytopenia Idiopathic neutropenia Leukopenia Lymphocyte count decreased Lymphopenia Metamyelocyte count decreased Monoblast count decreased Monocyte count decreased Monocytopenia Myeloblast count decreased Myelocyte count decreased Neutropenia

Neutropenic infection
Neutropenic sepsis
Neutrophil count decreased
Promyelocyte count decreased
Pure white cell aplasia
Radiation leukopenia
T-lymphocyte count decreased
White blood cell count decreased

Haematopoietic thrombocytopenia (SMQ-Narrow)

Acquired amegakaryocytic thrombocytopenia
Heparin-induced thrombocytopenia
Megakaryocytes decreased
Platelet count decreased
Platelet maturation arrest
Platelet production decreased
Platelet toxicity
Thrombocytopenia

Appendix 13

Patient Engagement Application

The Patient Engagement Application is a Smartphone system, referred to as an “app” that can be used by a patient or the legally authorized representative of a patient in the NP39761 study.

The app is an optional service that patients can opt-in to use to remind them of activities/task relevant to study compliances like when to take their study medication, attend site visit, track goals. The app also provides supportive guides to help patients be aware of visit procedures, study information and instructions.

The app’s interactive features are intended to be a companion to the user during the course of a trial and include the following modules:

- Study Information: targeted study information throughout the duration of the study.
- Visit Schedule: site visit reminder based on predefined Schedule of Assessments
- Goals: ability to implement study defined or personal goal targets (e.g., weight, exercise, sleep, etc.).
- Reminders: reminders for activities/task relevant to study compliances.
- Site Information: module where patients can enter their site contacts details.

The app is available for download to smartphone devices that support iOS or Android. The app will contain study-specific information only once activated by a patient. The study coordinator will provide the patient with a secure activation code, which they can use to activate the app upon their first use.

The app does not collect any patient-identified information or clinical data. This app is intended for informational purposes only. It is not a substitute for professional medical advice. Patients should contact the study site investigator or coordinator with any medical questions or concerns.

Appendix 14
Myeloproliferative Neoplasm Symptom Assessment Form Total Symptom Score (MPN-SAF TSS)

Myeloproliferative Neoplasm Symptom Assessment Form Total Symptom Score (MPN-SAF TSS)

Symptom	1 to 10 (0 if absent) ranking (1 is most favorable and 10 least favorable)
Please rate your fatigue (weariness, tiredness) by circling the one number that best describes your WORST level of fatigue during the past 24 hours	(No Fatigue) 0 1 2 3 4 5 6 7 8 9 10 (Worst Imaginable)
Circle the one number that describes how, during the PAST 24 HOURS how much difficulty you have had with each of the following symptoms	
Filling up quickly when you eat (Early Satiety)	(Absent) 0 1 2 3 4 5 6 7 8 9 10 (Worst Imaginable)
Abdominal discomfort	(Absent) 0 1 2 3 4 5 6 7 8 9 10 (Worst Imaginable)
Inactivity	(Absent) 0 1 2 3 4 5 6 7 8 9 10 (Worst Imaginable)
Problems with Concentration - Compared to prior to my MPD	(Absent) 0 1 2 3 4 5 6 7 8 9 10 (Worst Imaginable)
Night Sweats	(Absent) 0 1 2 3 4 5 6 7 8 9 10 (Worst Imaginable)
Itching (pruritus)	(Absent) 0 1 2 3 4 5 6 7 8 9 10 (Worst Imaginable)
Bone Pain (diffuse not joint pain or arthritis)	(Absent) 0 1 2 3 4 5 6 7 8 9 10 (Worst Imaginable)
Fever (>100 F)	(Absent) 0 1 2 3 4 5 6 7 8 9 10 (Daily)
Unintentional weight loss last 6 months	(Absent) 0 1 2 3 4 5 6 7 8 9 10 (Worst Imaginable)

Appendix 15
European Organization for Research and Treatment of Cancer
Quality of Life-Core 30 Questionnaire (EORTC QLQ-C30)

EORTC QLQ-C30 (version 3)

We are interested in some things about you and your health. Please answer all of the questions yourself by circling the number that best applies to you. There are no "right" or "wrong" answers. The information that you provide will remain strictly confidential.

	Not at All	A Little	Quite a Bit	Very Much
1. Do you have any trouble doing strenuous activities, like carrying a heavy shopping bag or a suitcase?	1	2	3	4
2. Do you have any trouble taking a long walk?	1	2	3	4
3. Do you have any trouble taking a short walk outside of the house?	1	2	3	4
4. Do you need to stay in bed or a chair during the day?	1	2	3	4
5. Do you need help with eating, dressing, washing yourself or using the toilet?	1	2	3	4
During the past week:				
	Not at All	A Little	Quite a Bit	Very Much
6. Were you limited in doing either your work or other daily activities?	1	2	3	4
7. Were you limited in pursuing your hobbies or other leisure time activities?	1	2	3	4
8. Were you short of breath?	1	2	3	4
9. Have you had pain?	1	2	3	4
10. Did you need to rest?	1	2	3	4
11. Have you had trouble sleeping?	1	2	3	4
12. Have you felt weak?	1	2	3	4
13. Have you lacked appetite?	1	2	3	4
14. Have you felt nauseated?	1	2	3	4
15. Have you vomited?	1	2	3	4
16. Have you been constipated?	1	2	3	4

Please go on to the next page

During the past week:

	Not at All	A Little	Quite a Bit	Very Much
17. Have you had diarrhea?	1	2	3	4
18. Were you tired?	1	2	3	4
19. Did pain interfere with your daily activities?	1	2	3	4
20. Have you had difficulty in concentrating on things, like reading a newspaper or watching television?	1	2	3	4
21. Did you feel tense?	1	2	3	4
22. Did you worry?	1	2	3	4
23. Did you feel irritable?	1	2	3	4
24. Did you feel depressed?	1	2	3	4
25. Have you had difficulty remembering things?	1	2	3	4
26. Has your physical condition or medical treatment interfered with your family life?	1	2	3	4
27. Has your physical condition or medical treatment interfered with your social activities?	1	2	3	4
28. Has your physical condition or medical treatment caused you financial difficulties?	1	2	3	4

For the following questions please circle the number between 1 and 7 that best applies to you

29. How would you rate your overall health during the past week?

1 2 3 4 5 6 7

Very poor

Excellent

30. How would you rate your overall quality of life during the past week?

1 2 3 4 5 6 7

Very poor

Excellent

Appendix 16
Patient Global Impression of Change (PGIC)

Patient Global Impression of Change

Since the start of the treatment you've received in this study, your polycythemia vera (PV) symptoms are (select one):

- Very much improved
- Much improved
- Minimally improved
- No change
- Minimally worse
- Much worse
- Very much worse

1. SCOPE OF THE DOCUMENT

The Module 2 of the Data Analysis Plan (DAP) is an internal working document by which the study statistician communicates to SPA, documentation specialist, clinical scientist, and other functions as appropriate (e.g., patient-reported outcomes specialist, clinical pharmacologist) information related to overall scope of the planned analysis and details related to data handling rules and output design (output specifications). Provision of a separate List of Planned Outputs (LoPO) allows early and effective communication of analysis scope. The output specifications include sufficient detail to enable the study lead SPA to implement these analyses.

DAP Module 2 (M2) is designed to meet scientific objectives, promote the use of standards, and encourage efficient use of resources. Module 2 consists of two components:

- List of Planned Outputs (LoPO)
- Output Specifications document

The Output Specifications contain the data handling rules and output specifications. Output requirements may be split in batches to allow SPAs to start work on the report section by section. This will allow batches of outputs to be produced in parallel, thus reducing overall timelines and resources. Biostatisticians are accountable for DAP M2.

2. LIST OF PLANNED OUTPUTS (LOPO)

The list of planned outputs (LoPO) contains a full list of all outputs needed for the clinical study report (CSR). It outlines the scope of analysis with reference to standard templates where applicable and priority. It also serves as an initial communication venue to discuss with clinical scientist to ensure the scope of analysis meets the scientific needs.

3. FILTERS, POPULATIONS AND SUBGROUPS

Filter Category	Label of population or subgroup	Filter	Description
Main Populations	Safety-Evaluable Patients	SE	All patients who received at least one dose of the study treatment, whether prematurely withdrawn from the study or not, will be included in the safety analysis.
	Intent-to-Treat Patients	IT	All enrolled patients, regardless of previous ruxolitinib treatment
	Primary Efficacy Patients	PE	Ruxolitinib-naive patients both with splenomegaly by imaging or without splenomegaly who have Completed at least 32 weeks of treatment or withdrew prior to Week 32 due to NR or progressive disease.
	Early-Look Efficacy Patients	ELE	Patients who have completed at least 3 and/or 5 cycles

	PK Patients	PK	All patients who have received at least one dose of study treatment and who have data from at least one post-dose sample will be included in the PK analysis population. Patients will be excluded from the PK analysis population if they significantly violate the inclusion or exclusion criteria, deviate significantly from the protocol, or if data are unavailable or incomplete which may influence the PK analysis. Excluded cases will be documented together with the reason for exclusion. All decisions on exclusions from the analysis will be made prior to database closure.
	Pharmacodynamic Patients	PD	All patients who had at least one pre-dose and one post-dose pharmacodynamic assessment will be included and analyzed.
	Prior Rux exposed patients	RUX	
	Patients with splenomegally	SPLNML	All patients with splenomegaly
	Patients without splenomegally	WOSPLML	
	All Rux naïve	RUXNAIVE	
Sub-setting of data by patient characteristics – key subgroups only	Patients aged >= 65	AGEGE65	Patients aged 65 or more

Additional filters are used to subset data based on assessments, e.g. serious adverse events or assessments during treatment.

4. DATA HANDLING SPECIFICATIONS

4.1 Reporting periods

The following definitions are used to allocate data to study periods. The same definitions are used for all outputs, e.g. AEs, laboratory data, patient disposition, unless otherwise specified.

4.1.1 Study Day 1

Original study day 1 is defined as the day of the first study treatment dose.

4.1.2 Before therapy

All events/assessments that occur before study day 1 are considered to have occurred before therapy and have a negative study day. AEs occurring at study day 1 are assumed to have occurred after therapy started. For handling of laboratory assessment, see definition of baseline.

4.1.3 Baseline

Baseline assessment is the last valid assessment before or on study day 1. As defined in the protocol, for all laboratory assessments at study day 1, it is assumed that the assessment was done before the treatment intake. The baseline will be kept throughout the entire study, i.e. there will be no new baseline derived if the dose is increased or decreased.

Baseline assessments that are measured only once at screening or week 1 and are not affected by treatment should be considered irrespective of the study day (e.g. gender, height, PV history).

4.1.4 Study cycles

A treatment cycle starts on the day of the first administration of study treatment and ends the day before the start of the next cycle. For example, cycle 1 will start at the first valid cycle 1 study drug administration and will end at the start date of the first cycle 2 dose minus 1 day. The last cycle ends when the treatment period ends.

4.1.5 Treatment period

Treatment period is defined as the time between Cycle 1 Day 1 and date of the clinical cutoff or the date of withdrawal or end of study, whichever comes first.

4.1.6 Observation time

Observation time is the time between date of enrollment (according to IxRS) and the date of withdrawal, study completion or cutoff whichever comes first (=last date known to be alive).

4.1.7 Last known alive date

The last known alive date is derived from the latest of dates in the following CRF fields: AE start and end dates, response assessment dates, study drug exposure dates, lab assessment dates, vital signs assessment dates, ECG assessment dates, death date, enrollment date and date of informed consent.

As per STREAM standard rules only partial dates from tumor response are included. In this case missing day is replaced by 1st of the month if only month and year are given. Dates where month and/or year are missing are not imputed but excluded.

4.1.8 Study Drug Exposure Time

Study drug exposure time is defined as last study drug administration date minus first study drug administration date plus one day.

4.1.9 Visits

The visits according to schedule of assessment are labeled as ‘Cycle x Day y’ (‘Cycle 1 Day 1’, ‘Cycle 2 Day 1’ etc.). Assessments are assigned to visits using the visit labels in SDTMv. In general, all summary tables by visit include all scheduled assessments as per SoA.

In case of multiple assessments per visit with a scheduled visit label, the visit with worst values is taken into account, otherwise the last visit is taken into account.

Note, in the majority of the summaries no ‘Cycle 1 Day 1’ is displayed because this is labeled as baseline.

If a Visit becomes a baseline value, it is only displayed as baseline. E.g. if ‘Cycle 1 Day 1’ is the baseline, then only Baseline is displayed in the outputs, followed by the next visit. In listings the original SDTMv visit label is shown.

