- 19 (-)3/(+)1 day window for Cycle 3 Day 28, Cycle 5 Day 28 and End of Cycle 8 (Week 32) and for every 3 cycles beyond. Must be prior to start of subsequent cycle. For the timepoint “End of Cycle 8” (Week 32), a patient experiencing a Dose Delay would perform the critical efficacy assessment(s) at whichever timepoint came first (Week 32 or End of Cycle 8) and performed assessment(s) would be recorded within the appropriate folder. In cases of dose delay where Week 32 occurs prior to the End of Cycle 8, any assessments performed at Week 32 would not need to be repeated at the End of Cycle 8.
- 20 Per modified 2009 ELN Criteria (see [Appendix 1](#)) for patients with splenomegaly at baseline. Solely Hct control for patients without splenomegaly at Baseline.
- 21 (-3) day window for COA; the questionnaires must be completed before the patient receives any information on disease status, prior to the performance of non-COA assessments, and prior to the administration of study treatment.
- 22 Hematology and Serum Chemistry need only be obtained once end of Cycles 3, 5, and 8, but pre-dose Cycles 4, 6, and 9 based on window in footnote 19. Ideally these Hematology and Serum Chemistry assessments will be done at the same time as all other Response assessments required at end of Cycles 3, 5, and 8.
- 23 COA questionnaires are only to be completed at Cycle 2 Day 1, not at Cycle 3 Day 1.

Table 2 Detailed Schedule of Activities

Cycle	Day	Hours Post Dose	ECG - 12 Lead	PK Sample ^a	PDy Serum MIC-1 ^a	Nucleic Acid Whole Blood ^{b, c}	Paxgene Whole Blood	Exploratory Biomarker PDy Flow Blood	TBNK Panel Flow Cytometry Blood	Cytokine Assay Plasma ^c	RBR DNA Optional ^d	RBR Serum Optional	
Cycle 1	Day 1	0 PreDose	x	x	x	x	x	x	x	x	x	x	
		1		x									
		2		x									
		4	x	x									
		6	x	x									
		10 ^e		x									
	Day 2	0/PreDose	x	x	x		x						
	Day 5	0 PreDose	x	x	x			x					
		1		x									
		2		x									
		4	x	x	x								
6		x	x	x									
10 ^e			x	x			x		x	x			
Cycle 2	Day 1	0 PreDose	x			x	x		x	x			
Cycle 3	Day 1	0 PreDose	x ^f			x							
		4	x ^f										
		6	x ^f										
	Day 2	24/PreDose	x ^f										
	Day 28 ^g	N/A				x				x			

Table 2 Detailed Schedule of Activities (cont.)

Cycle	Day	Hours Post Dose	ECG - 12 Lead	PK Sample ^a	PDy Serum MIC-1 ^a	Nucleic Acid Whole Blood ^{b, c}	Paxgene Whole Blood	Exploratory Biomarker PDy Flow Blood	TBNK Panel Flow Cytometry Blood	Cytokine Assay Plasma ^c	RBR DNA Optional ^d	RBR Serum Optional	

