8.2.1 Physical Examinations

A complete physical examination will include, at a minimum, assessments of the cardiovascular, respiratory, gastrointestinal, dermatological and neurological, musculoskeletal systems in addition to head, eyes, ears, nose, throat, neck and lymph nodes. Further examination of other body systems may be performed in case of evocative symptoms at the Investigator’s discretion.

Height at baseline and weight at each cycle will also be measured and recorded.

Performance status will be measured using the ECOG Performance Status Scale (Appendix 8).

Any abnormality identified at baseline should be recorded on the General Medical History and Baseline Conditions eCRF.

At subsequent visits (or as clinically indicated), limited, symptom-directed physical examinations should be performed. Changes from baseline abnormalities should be recorded in patient’s notes. New or worsened clinically significant abnormalities should be recorded as adverse events on the Adverse Event eCRF.

8.2.2 **Vital Signs**

Oral temperature, pulse rate, respiratory rate, and blood pressure will be assessed as outlined in the SoA (see Section 1.2).

Blood pressure and pulse measurements will be assessed in a supine position with a completely automated device. Manual techniques will be used only if an automated device is not available. When possible, the same arm should be used for all blood pressure measurements.

Blood pressure and pulse measurements should be preceded by at least 5 minutes of rest for the patient in a quiet setting without distractions (e.g., television, cell phones).

Vital signs (to be taken before blood collection for laboratory tests) will be measured in a supine position after 5-minute rest and will include temperature, systolic and diastolic blood pressure, pulse rate, respiratory rate and body temperature. Three readings of blood pressure and pulse will be taken. The first reading should be rejected. The second and third readings should be averaged to give the measurement to be recorded in the eCRF.

8.2.3 **Electrocardiograms**

Single 12-lead ECGs will be obtained as outlined in the SoA (see Section 1.2) using an ECG machine that automatically calculates the heart rate and measures PR, QRS, QT, and QTc intervals. The ECG should be confirmed as interpretable at site.

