To minimize variability, it is important that patients be in a resting position for ≥ 5 minutes prior to the ECG evaluation. Environmental distractions (e.g., television, radio, conversation) should be avoided during the pre-ECG resting period and during ECG recording. ECGs should be performed prior to any scheduled vital sign measurements and blood draws. In some cases, it may be appropriate to repeat abnormal ECGs to rule out improper lead placement as contributing to the ECG abnormality.

For safety monitoring purposes, the Investigator or designee must review, sign, and date all ECG tracings. Paper or electronic copies will be kept as part of the patient's permanent study file at the site. If considered appropriate by Roche, ECGs may be analyzed retrospectively at a central laboratory.

ECG characteristics, including heart rate, QRS duration, and PQ(PR), and QT intervals, will be recorded on the eCRF. QTcB (Bazett's correction), QTcF (Fridericia's correction) and RR will be recorded on the eCRF. Changes in T-wave and U-wave morphology and overall ECG interpretation will be documented on the eCRF. T-wave information will be captured as normal or abnormal, U-wave information will be captured in two categories: absent/normal or abnormal.

For Cycle 3 and beyond, ECGs must be done on Day 1 pre-dose, 4, 6 hours, and prior to the dose on Day 2 (24 hours post Day 1 dose) if there is evidence of QTc prolongation > 30 ms during Cycle 1 and Cycle 2 once the patient has received study medication as compared with the the QTcF interval of the screening ECG. Otherwise, ECGs will NOT be required for Cycle 3 and beyond unless the Investigator considers it necessary on behalf of the patient's safety. An unscheduled ECG can be performed as needed any time.

Allowed ECG sampling assessment windows are as follows:

- Pre-dose assessments: within 2 hours
- Assessments < 2 hours: ± 5 minutes
- Assessments 2–24 hours: $\pm 5\%$ (equal to 3 mins/hr)
- Assessments > 24 hours: ± 2 hours

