5.8.3 ECG and Vital signs

Vital signs will be summarized using mean change from baseline tables from baseline (VST01). All data is included in listings (UVSL01).

ECG parameters will similarly be summarized using mean change from baseline by visit (EGT01). Abnormal ECGs will be listed (UEGL01).

VST01/EGT01: Vital Signs Table

Vital Sign Results and Change from Baseline by Visit, <Specific Vital Sign>:
<Specify Population>
Protocol: xxnnnnn

Visit	Group 1 (N=nnn)	
	Value at Visit	Change from Baseline
Baseline		
N	nnn	
Mean (SD)	xx.x (xx.x)	
Median	xx.x	
Min-max	xx.x□xx.x	
Week xx		
n	nnn	nnn
Mean (SD)	xx.x (xx.x)	xx.x (xx.x)
Median	xx.x	xx.x
Min-max	xx.x □xx.x	xx.x□xx.x

UEGL_01: Listing of abnormal ECG

Listing of abnormal ECG: <Specify Patient Population with the Safety Evaluable Population as the default>

Protocol: xxnnnnn

Treatment: XXXX

Center/ Patient ID	Age/Sex/ Race	Study Day	Visit	ECG Result	Heart Rate (BPM)	msec						T Wave	U Wave
						P R	Q R	Q S	QT T	QT cB	QT cF		
[REDACTED]		1	SCREENING	ABNORMAL, NOT CLINICALLY SIGNIFICANT	59	114	118	94	390	400	NORMAL	ABSENT/NORMAL	
		60	WEEK 5	ABNORMAL, NOT CLINICALLY SIGNIFICANT	61	110	108	94	390	400	NORMAL	ABSENT/NORMAL	
		1	WEEK 1	ABNORMAL, NOT CLINICALLY SIGNIFICANT	55	118	108	94	390	407	NORMAL	ABSENT/NORMAL	

UVSL_01: Listing of Vital Signs

Listing of Vital Signs

Protocol: xxnnnnn

Treatment: XXXX

Center/ Patient ID	Age/Sex/ Race	Study Day	Visit	Systolic Blood Pressure [mmHg]	Systolic Blood Pressure [mmHg]	Pulse Rate [BEATS/MIN]	Respiratory Rate [BREATHS/MIN]	Temperature [C]	Weight [kg]
[REDACTED]		-1	SCREENING	xxx	xx	xx	xx	xx.x	xx.x
		60	WEEK 5	xxx	xx	xx	xx	xx.x	xx.x
		1	WEEK 1	xxx	xx	xx	xx	xx.x	xx.x

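### Read literally, the SAP's worst-value visit rule makes the Cycle 1 Day 5 QTc mean change a largest-of-three against one baseline reading, which is positive with no drug effect

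*SAP*

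**What the plan says.** SAP 4.1.9 names visits by cycle and day, with no hour after dosing. Where several assessments share a scheduled visit label, its rule is that "the visit with worst values is taken into account, otherwise the last visit is taken into account". The rule is not limited to any data type or table type.

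SAP 5.8.3 gives the ECG summary: "ECG parameters will similarly be summarized using mean change from baseline by visit (EGT01"). It states no exception to 4.1.9. The shell that EGT01 shares with vital signs has one block per visit and no row for time after dosing.

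Protocol Table 2 (Section 1.3) lists ECGs on Cycle 1 Day 5 at pre-dose, 4 h and 6 h; the Day 5 block opens with "Day 5 0 PreDose x x x". The 6 h row is shifted by a cell in the text available to us, but the pattern matches Day 1. Cycle 1 Day 2 and Cycle 2 Day 1 each have one ECG. Protocol 8.2.3 says: "Single 12-lead ECGs will be obtained as outlined in the SoA", so there are no triplicates. It also says "QTcB (Bazett's correction), QTcF (Fridericia's correction) and RR will be recorded on the eCRF".

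Under SAP 4.1.3, baseline is one reading: the most recent valid one up to and including Day 1. The statement that Day 1 values are taken to be pre-dose covers laboratory data only.

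**The concern.** A mean-change table should average to zero when nothing has changed. It does not if each patient's post-baseline value is picked as the most extreme of several and the baseline is not picked in the same way. On Day 5 the rule would also merge a pre-dose reading with two post-dose readings, so the row would not describe any one time after dosing.

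Day 5 is the last dosing day of the cycle. It is also the only routinely displayed visit with post-dose ECGs: SAP 4.1.9 shows Cycle 1 Day 1 only as baseline when it supplies the baseline, and from Cycle 3 ECGs are required only in patients with earlier QTc prolongation. The study has a single arm, so no control column would show the same artefact and allow it to be subtracted.

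**Working it through.** **Inputs from the documents**
- ECGs per label: 3 on Cycle 1 Day 5, 1 on Cycle 2 Day 1 (Protocol Table 2).
- Readings per time point: 1 (Protocol 8.2.3).
- Baseline: 1 reading, not a worst-of-several (SAP 4.1.3).
- Cohort size, used only for a standard error: about 20 (Protocol 9.2.1).

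**Assumptions not in the documents**
- Within-patient SD *s* of a single QTc reading: 5 to 15 ms.
- Normal errors, no drug effect, and worst taken as highest.

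The plan gives no QTc variability and no expected QTc change, so there is no figure of its own to reproduce.

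**Step 1: independent readings.** Let B be the baseline and X1, X2, X3 the Day 5 readings, all with the same mean. The tabulated change is max(X1, X2, X3) − B. Its expectation is *s* times the expected maximum of three standard normals, 3/(2√π) = 0.846. With one reading the factor is 0.

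| *s* (ms) | Spurious mean change, Day 5 (ms) | Cycle 2 Day 1 (ms) |
|---|---|---|
| 5 | 0.846 × 5 = 4.2 | 0 |
| 8 | 0.846 × 8 = 6.8 | 0 |
| 10 | 0.846 × 10 = 8.5 | 0 |
| 12 | 0.846 × 12 = 10.2 | 0 |
| 15 | 0.846 × 15 = 12.7 | 0 |

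**Step 2: correlated same-day readings.** If the three Day 5 readings share a day effect with correlation ρ, only the remaining part feeds the maximum, and the bias is 0.846 × *s* × √(1 − ρ). At *s* = 10 ms:
- ρ = 0.25: 8.46 × 0.866 = 7.3 ms
- ρ = 0.5: 8.46 × 0.707 = 6.0 ms
- ρ = 0.75: 8.46 × 0.5 = 4.2 ms

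The bias shrinks but stays positive unless the three readings are identical.

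**Step 3: against the noise in the table.** At *s* = 10 ms with independent readings, the SD of the change is √(7.48² + 10²) = 12.49 ms, where 7.48 ms is the SD of the maximum of three. With 20 patients the standard error is 12.49/√20 = 2.79 ms, so 8.46 ms is about 3 standard errors.

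**Step 4: does the baseline or the remedy change this?** A simulation of 1,000,000 patients with *s* = 10 ms and no drug effect gave these mean changes:
- Largest of three against the Day 1 pre-dose reading: 8.5 ms.
- Largest of three against the Day 1 6 h reading: 8.5 ms.
- Mean of the three Day 5 readings, or the last of them: 0.0 ms.
- Baseline also taken as the largest of three: 0.0 ms at Day 5, but −8.5 ms at Cycle 2 Day 1. SAP 4.1.3 does not define baseline this way.

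**The case against.** The strongest reply is that the pooling is an inference. Just before the rule, SAP 4.1.9 says that by-visit summaries cover every assessment scheduled. The Day 5 pre-dose, 4 h and 6 h ECGs are separate entries in Table 2, so each might get its own row, leaving the worst-value rule for true repeats, which Protocol 8.2.3 allows. The SAP does work at time-point level for total neutrophils (5.8.4.2). The EGT01 shell is generic, and the List of Planned Outputs and DAP Module 3 are not available here. This reading is possible, and for that reason the point is put as what the text yields when read literally. But the visit labels carry no hour, the shell has no hour row, 5.8.3 has no override, and documents we cannot see cannot be assumed to settle it.

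Second, the clause "the visit with worst values is taken into account, otherwise the last visit is taken into account" may mean worst where a worst direction exists and last where it does not. That would cover heart rate and PR, so no bias is claimed for them; the wording is merely unclear. Potassium would be a poor example, since chemistry is drawn once per visit day. Blood pressure and pulse repeats are already averaged under Protocol 8.2.2.

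Third, the analysis is descriptive, individual ECG listings are planned, and an overstated QTc rise errs towards caution. This limits the importance but does not make the row interpretable.

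A reader might also infer that the rule inflates the share of patients above the protocol's 30 ms threshold. The documents do not support that. EGT01 has no such row, and the protocol applies the threshold to individual ECGs against screening, outside SAP 4.1.9. A shell with millisecond categories does appear in SAP 5.7.3.1, but under molecular response and tied to no ECG output.

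**Conclusion.** The point holds on the literal text. As written, the rule gives a positive QTc mean change at Cycle 1 Day 5 with no drug effect, and a value that cannot be set beside Cycle 2 Day 1. The sign needs only that worst means highest and that the three readings are not identical. The size is conditional: 4.2 to 12.7 ms for an assumed SD of 5 to 15 ms with independent readings, and less with same-day correlation.

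The scope is narrow. Day 5 is the displayed visit affected for all patients; Cycle 1 Day 2 has one scheduled ECG and is not affected. Later visits with several ECGs concern only patients who met the QTc condition. Two wider inferences are not supported. Nothing in the documents calls Day 5 the main ECG evidence of the trial. Nor does the choice of baseline act in a known opposite direction: with no drug effect it has none, and the bias is the same for a pre-dose or a 6 h baseline. This is a safety summary and does not touch the primary endpoint. It should be corrected before the tables are programmed.

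**What to change.** In SAP 4.1.9 and 5.8.3:
- Tabulate ECG change by nominal time point wherever a visit day has more than one scheduled ECG: Day 5 pre-dose, 4 h and 6 h, and the Day 1 post-dose readings if they are shown.
- State that the ECG baseline is a pre-dose reading, since the present pre-dose assumption covers laboratory data only.
- Use the scheduled or last valid value, not the worst, in all mean-change tables.
- Keep worst value for shift and outlier tables only, with the direction stated for each parameter.

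The hours are already in the schedule, so no new data are needed. The cost is SAP wording and a few more table rows. With no drug effect, the expected change in each row is then zero.
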